5.3.2. General Data Handling Rules

Missing data will be handled depending on the assumed mechanism behind the missingness, whether the endpoint is a key endpoint, and the estimand being used. Handling rules are summarized in Table 5 below:

Table 5: Data Handling Rules for Missing Data

Estimand	imand Assumption Continuous endpoints		Binary response endpoints
Estimand	Assumption MAR (Missing at Random) due to Natural Disaster or Major Disruption MAR NOT due to	Continuous endpoints Major secondary endpoint: imputed using Full Conditional Specifications (FCS) MI Clinical Other endpoints: not imputed but accounted for in MMRM model Major secondary endpoints:	Binary response endpoints Primary and Major secondary endpoints: imputed using Full Conditional Specifications (FCS) MI on continuous component scale then dichotomized Clinical Other endpoints: not imputed but accounted for in GLMM Primary and Major secondary
Adjusted Composite	above reasons	imputed using Full Conditional Specifications (FCS) MI Clinical Other endpoints: not imputed but accounted for in MMRM model	endpoints: conservatively imputed as non-response for consistency with historical studies Clinical Other endpoints: conservatively imputed as non-response for consistency with historical studies
	Missing Not at Random (MNAR)	N/A	Primary endpoints: For tipping point analyses specifically: Sensitivity analysis with exhaustive assessment of all possible combinations of response status for missing data
	MAR	Major secondary endpoints: imputed using FCS MI	Primary and Major secondary endpoints: imputed using FCS MI on continuous component scale then dichotomized
Treatment Policy	MNAR	Major secondary endpoints: For tipping point analyses specifically: Supplementary analysis systematically assessing scenarios which deviate from MAR or MCAR assumption	Primary and Major secondary endpoints: For tipping point analyses specifically: Supplementary analysis systematically assessing scenarios which deviate from MAR or MCAR assumption
	MCAR	Other Efficacy endpoints: not imputed	Other Efficacy endpoints: not imputed

5.3.2.1. MI Using FCS Regression

Under the assumption of MAR, MI will be used to impute the missing data for the continuous/ordinal measurements. The missing data will be imputed using the predicted value from an imputation model using the Full Conditional Specification (FCS) regression method for any missing pattern. Each variable will be restricted to only impute within its possible range of values (eg, HAQ Score may only be imputed to within 0-3). The explanatory variables in the imputation model include imputation variables and ancillary variables as specified in Section 6.12 (Appendix 12).

The number of imputations (N) and the starting seeds are also specified in Section 6.12 (Appendix 12).

For the composite continuous endpoints, the above imputation will be performed on components with missing data and then composite score will be derived based on such imputed components.

For categorical endpoints (such as IGA response), the above imputation will be performed for the respective scores on a continuous scale, then rounded to the nearest integer prior to deriving the response or resolution.

For the composite binary endpoints (such as ACR 20), the above imputation will be performed on each component with missing data and then response status will be determined based on such imputed components.

The treatment comparisons between a guselkumab group versus the placebo group will be performed using the analysis method specified for each of the N imputation datasets. The analysis results from all the N imputation datasets will be combined according to Rubin (Rubin 1987) and the p-value for testing the treatment difference will be obtained.

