8.1.1.9. Minimal Disease Activity

The PsA minimal disease activity (MDA) criteria are a composite of 7 outcome measures used in PsA. Participants are classified as achieving MDA if they fulfill 5 of 7 outcome measures: tender joint count ≤ 1 ; swollen joint count ≤ 1 ; psoriasis activity and severity index ≤ 1 ; patient pain VAS score of ≤ 15 ; patient global disease activity VAS (arthritis and psoriasis) score of ≤ 20 ; HAQ score ≤ 0.5 ; and tender entheseal points ≤ 1 (Coates, 2010).

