6.12. Appendix 12: Summary of Analyses Based on Multiple Imputation

Summary of Multiple Imputation Method

Endpoints (Population ^a) Estimand ^b	MI specification	Analysis method/Summary statistics	
ACR20 at Week 24 ACR20 at Week 16 ACR50 at Week16 and Week24 ACR70 at Week24 HAQ-DI Score (FAS) Adjusted Composite Estimand (FAS-UKR) Treatment Policy Estimand	Multiple imputation with FCS regression of component scores	MIdata1 (N=200, Seed ^d =18496) • Imputation variables: 7 ACR components from Week 0-Week24 • Ancillary variables: Intervention group, baseline non-biologic DMARD use (yes/no)	
PASI 90 response at Week 24 among subjects with ≥3% BSA psoriatic involvement and an IGA score of ≥2 (mild) at baseline (FAS) Adjusted Composite Estimand (FAS-UKR) Treatment Policy Estimand	Multiple imputation with FCS regression of component scores	MIdata2 (N=200, Seed ^d =6509723) Note: The MI is done only for the subset of subjects who have ≥3% BSA psoriatic involvement and an IGA score of ≥2 (mild) at baseline, and not all subjects in the study population. ■ Imputation variables: PASI score from Weeks 0-24 ■ Ancillary variables ^c : Intervention group, baseline non-biologic DMARD use (yes/no), 7 ACR components from Weeks 0-24	
Achieving MDA At week24 (FAS) Adjusted Composite Estimand (FAS-UKR) Treatment Policy Estimand	Multiple imputation with FCS regression of component scores	MIdata3 (N=200, Seed ^d =6509723) • Imputation variables: 7 MDA components from Week 0-24 • Ancillary variables: Intervention group, baseline non-biologic DMARD use (yes/no)	
Change from baseline through Week 24 in: • PCS score • Facit-F score (FAS) Adjusted Composite Estimand (FAS-UKR) Treatment Policy Estimand	Multiple imputation with FCS regression of PC	MIdata4 (N=200, Seed ^d =890473) • Imputation variables: PCS scores and Facit-F scores from Weeks 0–24 • Ancillary variables ^c : Intervention group, baseline non-biologic DMARD use (yes/no), 7 ACR components from Weeks 0-24	

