IGA change from baseline through Week 24 among subjects with ≥3% BSA psoriatic involvement and an IGA score of ≥2 at baseline (FAS) Adjusted Composite Estimand (FAS-UKR) Treatment Policy Estimand a The population defines which s	Multiple imputation with FCS regression of IGA scores	MIdata5 (N=200, Seed ^d = 413249) Note: The MI is done only for the subset of subjects who have ≥3% BSA psoriatic involvement and an IGA score of ≥2 (mild) at baseline, and not all subjects in the study population. • Imputation variables: IGA scores from Weeks 0–24 Ancillary variables ^c : Intervention group, baseline non-biologic DMARD use (yes/no) 7 ACR components from Weeks 0-24 will be performed for.	

- ^b The handling of ICEs associated with the estimand listed will be applied to the imputation variables and ancillary variables (if post-baseline) prior to imputation.
- ^c An ancillary variable may be removed if its correlation with an indicator variable that determines missing-ness of the variable to be imputed is low or, there are too many missing values for the ancillary variable within the subgroup of incomplete cases for the variable to be imputed. All the 7 ACR components (including all measurements from baseline through Week 24) are in the list of the ancillary variables since they may be related to the mechanism leading to missing data.
- ^d The starting seed for FCS regression MI is used to generate a series of imputation seeds using the algorithm: INT((2**31-2)*RANUNI(starting seed)), where each imputation seed will be used for a single imputation. To account for the possibility that some imputations may fail to complete due to out-of-range issues, 200+ initial imputation seeds will be prepared, and the first 200 successful imputations will be used for analysis.

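### Range-bounded linear imputation of skewed components understates response among imputed guselkumab participants, most for MDA, with a bias that scales with an unstated imputed share

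*SAP*

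**What the plan says.** SAP 5.3.2.1 states that missing values are "imputed using the predicted value from an imputation model using the Full Conditional Specification (FCS) regression method for any missing pattern", and adds: "Each variable will be restricted to only impute within its possible range of values (eg, HAQ Score may only be imputed to within 0-3". For composite binary endpoints, "the above imputation will be performed on each component with missing data and then response status will be determined based on such imputed components". Rounding to an integer is specified only for categorical scores such as IGA. No transformation or matching step is given for joint counts, CRP, PASI or entheses.

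Appendix 12, note d, anticipates that "some imputations may fail to complete due to out-of-range issues", and resolves this by rule: "the first 200 successful imputations will be used for analysis". The MDA imputation uses "7 MDA components from Week 0-24". Protocol 8.1.1.9 defines the endpoint: "Participants are classified as achieving MDA if they fulfill 5 of 7 outcome measures". Those measures include tender joints, swollen joints, tender entheses and PASI, each at most 1.

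The scope of imputation depends on the estimand:
- **Main (Adjusted Composite), binary endpoints** (SAP 5.3.4.3, 5.3.5.9): imputation covers data after ICE 4/5 and data missing because of Natural Disaster or Major Disruption. ICE 1-3 and all other missing data count as non-response.
- **Treatment Policy, primary and major secondary endpoints** (Table 5): all missing data are imputed.
- **Treatment Policy, Other Efficacy endpoints** (Table 5, 5.3.6.2.9): nothing is imputed.

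**The concern.** MDA is decided close to the floor of several scales. If many treated participants have zero or one affected joint, a normal linear model cannot reproduce that pile-up. Draws confined to the positive range spread upward and seldom fall at 0 or 1. Imputed participants on guselkumab then respond less often than similar observed participants do. Placebo has fewer near-floor responses to lose, so the treatment difference shrinks.

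MDA belongs to the strongly controlled sequence, and its q8w comparison has the lowest planned power there (78%, Table 4). ACR 50 and ACR 70 are only weakly controlled.

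Keeping only imputations that complete is a further concern in principle. Rubin's rules, cited in SAP 5.3.2.1, presume that draws were not selected by their outcome.

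**Working it through.** **1. Reproduce the plan's figure.** Inputs from SAP Table 4, MDA q8w from PSA3001: p1 = 0.111, p2 = 0.228, n = 150 per arm, two-sided alpha 0.05.

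Power = Phi{[d·√n - 1.96·√(2·pbar·(1-pbar))] / √(p1q1 + p2q2)}, with d = 0.117 and pbar = 0.1695.

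= Phi{(1.433 - 1.040) / 0.524} = Phi(0.750) = 77.3%, against 78% stated.

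The other MDA rows give 98.8% (stated 99%) and 94.8% (95%). ACR 70 q8w gives 44.2% (44%).

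**2. Simulate the imputation rule.** The documents give no component distributions, number imputed or timing of missingness, so these are assumptions. Components were imputed by chained linear regression with draws truncated to range, with arm and DMARD use as ancillary variables, and response was then derived. The imputed share was 5%. Response rates among imputed participants with floor-heavy data:

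| Endpoint | Weeks missing | q8w true / imputed | q4w true / imputed | Bias in difference, q8w / q4w (points) |
|---|---|---|---|---|
| MDA | 24 | 18% / 4% | 24% / 7% | -0.47 / -0.67 |
| MDA | 16-24 | 20% / 1% | 30% / 3% | -0.58 / -0.97 |
| ACR 70 | 24 | 11% / 5% | 16% / 6% | -0.27 / -0.42 |
| ACR 70 | 16-24 | 11% / 3% | 18% / 4% | -0.33 / -0.61 |
| ACR 50 | 24 | 22% / 14% | 31% / 20% | -0.25 / -0.43 |
| ACR 50 | 16-24 | 24% / 13% | 37% / 18% | -0.31 / -0.68 |
| ACR 20 | 24 | 48% / 40% | 53% / 42% | -0.25 / -0.40 |
| ACR 20 | 16-24 | 46% / 34% | 60% / 43% | -0.22 / -0.49 |

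Hand check of the first row, where placebo MDA was 4% true and 0% imputed: bias ≈ f × [(imputed - true, active) - (imputed - true, placebo)] = 0.05 × [(4 - 18) - (0 - 4)] = -0.5 points.

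With a lighter floor, MDA was 11-14% true against 1-3% imputed, with bias -0.31 to -0.53. A more responsive data set with 10% missing gave MDA bias of -1.7 to -2.9.

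**3. Compare alternatives (floor-heavy, Week 24 missing, MDA true / imputed).**
- Predictive mean matching: 20% / 19% (q8w) and 27% / 24% (q4w).
- Unbounded regression: 24% / 15% and 28% / 18%, so lifting the bound alone is not enough.

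Two simulations of joint counts alone agree. For at most 1 tender and 1 swollen joint, truth / bounded / matching was 25% / 2% / 22% in one and 13% / 1% / 12% in the other. Matching with arm as a covariate did as well as matching within arm (12% each). In the first, the 20% joint improvement was 77% / 76% / 78%.

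**4. Worst case for power.** If a share f of each arm is imputed and none respond, both rates are multiplied by (1 - f). For MDA q8w:
- f = 2%: difference 11.7 × 0.98 = 11.5 points, power 76.3%
- f = 5%: 11.1 points, power 74.7%
- f = 10%: 10.5 points, power 72.0%

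**5. Coverage by planned sensitivity analyses.** The tipping point under the main estimand (SAP 5.3.2.2.1) is for ACR 20 only and holds ICE 4/5 imputations fixed. For MDA and ACR 50/70, tipping points run under Treatment Policy on FAS-UKR (Table 7), which excludes Ukrainian sites, and their deltas start from rates produced by the same imputation model.

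**The case against.** The strongest reply is scope. In the main binary analyses most missing data are non-response by rule, so few participants may be imputed. The documents give no count. The error is conservative, and MDA is last in the fixed sequence, so no later test is lost. The Treatment Policy tipping points shift the imputed response rates directly. All of this stands, and it limits the size of the problem. It does not make the model fit, and those tipping points do not reach the main estimand.

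A second reply is that matching within arm would be heavy: 7 ACR components at 7 visits is 49 variables on 150 participants, and fewer participants in the skin subset. That is fair against within-arm models, but keeping arm as a covariate avoids it.

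A reader might also infer more than the documents support:
- **That imputed participants almost never reach ACR 50 or ACR 70.** These criteria are relative to baseline. Imputed rates were roughly half to three quarters of truth for ACR 50 and a quarter to three quarters for ACR 70. ACR 50 came near zero only with all visits from Week 8 missing. Matching also did poorly on MDA there, and short chains make those runs unreliable.
- **That every Treatment Policy analysis is affected.** Other Efficacy endpoints are not imputed.
- **That discarding failed imputations drives the bias.** The shortfall arose with none discarded. An estimated 11-23% of imputations would fail if each value were allowed 100 redraws (an assumption), but the added effect was not isolated.
- **That PASI 90 and IGA are biased too.** Neither was shown, and IGA is rounded before response is derived.

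**Conclusion.** The concern holds in limited form. For skewed components that pile up at the floor, bounded linear imputation understates response among imputed guselkumab participants. The effect is largest for MDA (about 18-30% true against 1-7% imputed under floor-heavy assumptions) and smaller for ACR 70 and ACR 50. ACR 20 is proportionately least affected: almost nothing on joint counts alone, and 0.2-0.5 points on the full endpoint at 5% imputed.

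In the main analysis the bias scales with the unstated share of participants with ICE 4/5 or disruption-related missing data. At 5%, the MDA difference loses about 0.3 to 1.0 points, against planned differences of 11.7 to 19.4. Worst-case q8w power falls from 77.3% to 74.7%. The supplementary Treatment Policy analyses of the primary and major secondary endpoints carry the same bias.

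The sizes rest on assumed distributions, shares and timing, in a small simulation. Joint counts were not rounded; rounding would raise the rate of meeting a count of at most 1. The direction was consistent for MDA and the joint floor across the data sets tried.

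**What to change.** In SAP 5.3.2.1 and Appendix 12, replace bounded regression with FCS predictive mean matching for the ACR components, the MDA components and PASI. Keep intervention group as a covariate, and match within arm only where donors suffice. State the number of donors and the matching scale. Imputed values are then observed values and always in range, so delete the range restriction and the rule on successful imputations for these variables. Report the number of participants imputed per arm, by reason, for each endpoint.

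The cost is a change of imputation method in the code plus SAP wording. The small downside is fewer close donors in the skin subset.

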5.3.2.2. Imputing Missing Data Evaluating Deviation from Assumptions (Tipping Point Analyses)

5.3.2.2.1. For Primary Endpoint

For the **Primary endpoint** (ACR 20 response at Week 24) using the Adjusted Composite Estimand (see Section 5.3.4.2 for definition of estimand), the exhaustive scenario tipping point analyses will be performed to evaluate any deviation from the imputation of: missing NOT due to Natural Disaster or Major Disruption (see Section 5.3.4.2) being imputed as non-responder, and missing due to Natural Disaster or Major Disruption being imputed using FCS MI under MAR assumptions.

Note that as part of the ICE strategies for the Adjusted Composite Estimand (see Section 5.3.4.2), participants who meet ICEs 1-3 prior to Week 24 are set to non-responder regardless of observed data, and participants who meet ICEs 4 or 5 prior to Week 24 are imputed using FCS MI regardless of observed data. These participants, combined with participants with observed data at Week 24 who did not meet any ICEs prior that timepoint, comprise the not-to-be-varied group for the Adjusted Composite Estimand, and their response rate remains static through the tipping point analysis.

Let T_A be the total number of imputed values to-be-varied in the Active arm, where i of them will be set to 'Yes' response and (T_A-i) of them set to 'No' response. In the same vein, let T_P be the total number of imputed values to-be-varied in the Placebo arm, where j of them will be set to 'Yes' response and (T_P-j) of them set to 'No' response. The range of i is from 0 to T_A , and a range of j is from 0 to T_P , which is an 'exhaustive approach'.

Also for the **Primary endpoints** but using the Treatment Policy Estimand (see Section 5.3.4.2 for definition of estimand), the tipping point analyses based on imputed data by FCS MI will be performed to evaluate the impact of imputed when deviating from the MAR assumption.

- A pair of deltas (eg, Dg =-0.1, Dp =0.2) will be added to the predicted response rates of each missing data from the MI method depending on guselkumab or placebo group.
- With the new response rate, the missing response will be imputed for N (eg, N=200) times to generate N multiple imputations based on a Bernoulli distribution. Treatment comparisons will then be performed same as treatment comparison with MI.
- The range of delta values includes the scenarios where participants on guselkumab have worse outcomes than participants on placebo.

The Treatment Policy Estimand considers the ICEs irrelevant to the endpoint, thus all the missing data in the specified analysis population will be imputed and will comprise the to-be-varied group.

5.3.2.2.2. For Major Secondary Endpoints

For the **major secondary binary endpoints**, using the Treatment Policy Estimand (see Section 5.3.4.2 for definition of estimand), the tipping point analyses based on imputed data by FCS MI will be performed to evaluate the impact of imputed when deviating from the MAR assumption.

Note that as part of the ICE strategies for the Treatment Policy Estimand (see Section 5.3.4.2), the observed response for all participants will be used regardless of whether or not ICE criteria are met prior to Week 24. These participants comprise the not-to-be-varied group, and their response rates remain static through the tipping point analysis. The method of imputation is same with the tipping point analyses for Primary endpoints using the Treatment Policy Estimand.

For the **Major Secondary continuous endpoints** (change from baseline to Week 24 in HAQ-DI/SF-36 PCS/FACIT-F score) using the Treatment Policy Estimand (see Section 5.3.4.2), the tipping point analyses based on imputed data by FCS MI will be performed to evaluate the impact of imputed data when deviating from the MAR assumption.

- A delta (eg, Dg=0.2, Dp=0.1) will be added to the imputed value for each participant with missing value from the MI depending on whether the participant is in the guselkumab or placebo group.
- With the new datasets, treatment comparisons will be performed similar to treatment comparisons with MI data.
- The analysis will be repeated for a range of Dg and Dp by varying Dg and Dp independently, including the scenarios where participants on guselkumab have worse outcomes than participants on placebo.

5.3.3. Analysis Specifications

5.3.3.1. Level of Significance

In general, statistical testing will be performed using 2-sided tests. The overall Type I error will be controlled among the primary and major secondary endpoints at 5%.

5.3.3.2. Multiplicity Adjustment for Testing Procedures

This study has 1 primary endpoint (proportion of participants who achieved an ACR 20 response at Week 24) and 10 major secondary endpoints. With 11 endpoints and 2 treatment comparisons for each of these endpoints, there are a total of 22 hypotheses to be tested. These hypotheses are explicitly listed in Section 6.11.

The overall Type I error of the 22 hypotheses will be controlled at a significant level of ≤ 0.05 . The testing procedure tests the primary and selected major secondary endpoints, for the two regimens of guselkumab vs placebo, in a fixed sequence and each endpoint is tested at the two-sided 0.05 level of significance. The fixed sequence testing method tests an endpoint only if the null hypotheses of no difference between the gulsekumab regimen and placebo were rejected at the 0.05 level for all the endpoints above it in the sequence. This is shown visually in Figure 2 below.

Multiplicity Control Figure 2: Primary Endpoint ACR20 response at Week 24 (q4w vs placebo) If p≤0.05 ACR20 response at Week 24 (q8w vs placebo) If p≤0.05 Major Secondary Endpoints IGA response at Week 24 (q4w vs placebo) If p≤0.05 IGA response at Week 24 (q8w vs placebo) If p≤0.05 PASI 90 response at Week 24 (q4w vs placebo) If p≤0.05 PASI 90 response at Week 24 (q8w vs placebo) If p≤0.05 Change from baseline to Week 24 in HAQ-DI (q4w vs placebo) If p≤0.05 Change from baseline to Week 24 in HAQ-DI (q8w vs placebo) If p≤0.05 Change from baseline to Week 24 in SF-36 Physical Component Score (q4w vs placebo) If p≤0.05 Change from baseline to Week 24 in SF-36 Physical Component Score (q8w vs placebo) If p≤0.05 Change from baseline to Week 24 in FACIT-F (q4w vs placebo) If p≤0.05 Change from baseline to Week 24 in FACIT-F (q8w vs placebo) If p≤0.05 Achieving MDA at Week 24 (q4w vs placebo) If p≤0.05 Achieving MDA at Week 24 (q8w vs placebo)

For the weakly controlled hypothesis tests (see Section 3.2), p-values are not strictly controlled. However, as its test depends on the positive result of its correlated strongly controlled hypothesis test, there are some levels of control even though the level of control is not quantifiable. Although

the level of control is not quantifiable, these reported p-values are not considered nominal. As a result, p-value for the weakly controlled hypothesis test will be reported with a footnote. The footnote will state that the test is not part of the sequential testing procedures but was prespecified to be tested upon achieving statistical significance of the strongly controlled primary endpoints.

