Safety assessments will consist of physical examinations, vital signs, height and weight, electrocardiograms, clinical safety laboratory assessments, suicidal ideation or behavior using the electronic Columbia-Suicide Severity Rating Scale (eC-SSRS), and concomitant medication review. Injection site reactions, hypersensitivity reactions, infections, tuberculosis evaluations and pregnancy testing will be collected or performed as specified in the Schedule of Activities.

STATISTICAL METHODS

A sample size of 150 participants per group for each of the guselkumab treatment groups and placebo will have >90% power to detect differences between each guselkumab treatment group and placebo for the primary endpoint assuming a 2-sided alpha level of 0.05.

In general, descriptive statistics, such as mean, standard deviation (SD), median, interquartile (IQ) range, minimum, and maximum for continuous variables, and counts and percentages for discrete variables will be used to summarize most data. For binary response efficacy endpoints, treatment comparisons will generally be performed using a Chi-square test or a Cochran-Mantel-Haenszel (CMH) test. For continuous endpoints of efficacy data, treatment comparisons will be performed using an analysis of covariance (ANCOVA), a mixed model for repeated measures (MMRM) or a constrained longitudinal data analysis (cLDA) model.

In general, statistical testing will be performed using 2-sided tests. The overall type I error will be controlled among the primary and major secondary endpoints at 5%.

[figure not shown]
The primary endpoint to be analyzed for the primary analysis is the proportion of participants who achieved an ACR 20 response at Week 24. This endpoint will be analyzed based on the estimands defined in Section 9. Participants with missing data at Week 24 will be considered non-responders.

The Type 1 error will be multiplicity controlled for the primary and major secondary endpoints. All other secondary endpoints will be summarized over time by treatment groups. Treatment comparisons will be performed by visit through Week 24.

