6.10. Appendix 10: Statistical Hypothesis

Hypothesis	Control
Primary Endpoints	
H1. Guselkumab 100 mg q4w SC is superior to	Controlled as in Figure 2
placebo as assessed by the proportion of subjects	
achieving an ACR 20 response at Week 24 (primary	
hypothesis)	
H2. Guselkumab 100 mg at Week 0, Week 4, then	Controlled as in Figure 2
q8w SC is superior to placebo as assessed by the	
proportion of subjects achieving an ACR 20 response	
at Week 24	
Major Secondary Endpoints	
H3. Guselkumab 100 mg q4w SC is superior to	Controlled as in Figure 2
placebo as assessed by proportion of subjects who	
achieved a psoriasis IGA response at Week 24 among	
the subjects with ≥3% BSA psoriatic involvement and	
an IGA score of ≥2 (mild) at baseline	
H4. Guselkumab 100 mg at Week 0, Week 4, then	Controlled as in Figure 2
q8w SC is superior to placebo as assessed by	
proportion of subjects who achieved a psoriasis IGA	
response at Week 24 among the subjects with ≥3%	
BSA psoriatic involvement and an IGA score of ≥2	
(mild) at baseline	
H5. Guselkumab 100 mg q4w SC is superior to	Controlled as in Figure 2
placebo as assessed by proportion of subjects who	
achieved PASI 90 response at Week 24	
H6. Guselkumab 100 mg at Week 0, Week 4, then	Controlled as in Figure 2
q8w SC is superior to placebo as assessed by	
proportion of subjects who achieved PASI 90 response	
at Week 24	
H7. Guselkumab 100 mg q4w SC is superior to	Controlled as in Figure 2
placebo as assessed by change from baseline in HAQ-	
DI score at Week 24	
H8. Guselkumab 100 mg at Week 0, Week 4, then	Controlled as in Figure 2
q8w SC is superior to placebo as assessed by change	
from baseline in HAQ-DI score at Week 24	

TTO C 11 1 100 4 CC 1 1 4	C + 11 1 ' E' 2
H9. Guselkumab 100 mg q4w SC is superior to	Controlled as in Figure 2
placebo as assessed by change from baseline in SF-36	
PCS at Week 24	
H10. Guselkumab 100 mg at Week 0, Week 4, then	Controlled as in Figure 2
q8w SC is superior to placebo as assessed by change	
from baseline in SF-36 PCS at Week 24	
H11. Guselkumab 100 mg q4w SC is superior to	Controlled as in Figure 2
placebo as assessed by change from baseline in Facit-	
F at Week 24	
H12. Guselkumab 100 mg at Week 0, Week 4, then	Controlled as in Figure 2
q8w SC is superior to placebo as assessed by change	_
from baseline in Facit-F at Week 24	
H13. Guselkumab 100 mg q4w SC is superior to	Controlled as in Figure 2
placebo as assessed by proportion of subjects who	
achieved MDA at Week 24	

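### The SAP claims 5% Type I error control over 22 hypotheses, but its testing sequence covers only 14

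*SAP*

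**What the plan says.** SAP 5.3.3.1 makes the general claim: "The overall Type I error will be controlled among the primary and major secondary endpoints at 5" percent. SAP 5.3.3.2 counts 11 endpoints by two comparisons and extends the claim to all of them: "The overall Type I error of the 22 hypotheses will be controlled at a significant level of" ≤0.05. Protocol 9.1 promises family-wise control at 0.05 and leaves the method to the SAP. Protocol 9.4.1 repeats the 5% statement. The protocol synopsis repeats it too, and adds "The Type 1 error will be multiplicity controlled for the primary and major secondary endpoints".

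The procedure itself is a fixed sequence, each test at two-sided 0.05, for the primary endpoint and only some of the major secondary endpoints. Figure 2 ends at MDA, q8w versus placebo. Appendix 10 (SAP 6.10) marks H1–H14 as controlled through Figure 2 and H15–H22 as weakly controlled.

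Below Figure 2 the SAP qualifies the remaining eight: "For the weakly controlled hypothesis tests (see Section 3.2), p-values are not strictly controlled". It relies on a gate, "as its test depends on the positive result of its correlated strongly controlled hypothesis test", and then says that although "the level of control is not quantifiable, these reported p-values are not considered nominal". A footnote must accompany these p-values. It says that the test is outside the sequence and "was prespecified to be tested upon achieving statistical significance of the strongly controlled primary endpoints".

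**The concern.** Control at ≤0.05 over 22 hypotheses and unquantifiable control over eight of those 22 cannot both be true. A fixed sequence protects only the hypotheses in it. A gate on ACR20 at Week 24 protects the others only while the ACR20 null is true. Once ACR20 truly works, which is what the trial is powered to show, the gate is open and the eight tests run with nothing shared between them.

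The gate is also incompletely specified. Both descriptions of it most naturally mean ACR20 at Week 24, the only ACR endpoint in Figure 2. One description is singular and the other plural, and Appendix 10 puts both H1 and H2 under the heading "Primary Endpoints". If q4w succeeds on ACR20 and q8w fails, the SAP does not say whether the q4w tests among H15–H22 go ahead.

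At stake is how an ACR50 or ACR70 result may be described. The 22-hypothesis sentence, together with the statement that these p-values are not nominal, would support presenting such a result as part of a 5% family when it is not.

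**Working it through.** **Counting.** Total: 11 endpoints × 2 regimens = 22. In Figure 2: ACR20 at Week 24, IGA, PASI 90, HAQ-DI, SF-36 PCS, FACIT-F and MDA, so 7 × 2 = 14. Outside it: 4 × 2 = 8.

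**The plan's own figure.** In a fixed sequence with every test at two-sided 0.05, a false rejection requires rejecting the first true null reached. The family-wise error is therefore at most 0.05, and the stated level reproduces for H1–H14. It also holds for all 22 if the H1 null is true, because every later test is reached only after H1 is rejected. That is control in the weak sense only.

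**When ACR20 at Week 24 is truly effective.** Inputs and assumptions:
- The gate is passed with probability about 1. SAP Table 3 gives power above 99% for both regimens.
- Each of H15–H22 is tested at two-sided 0.05. The SAP does not state this; it is inferred from the p=0.05 in the power column of Table 4.
- The correlation between the two regimens' statistics is 0.5. With equal arms, the shared placebo contributes covariance σ², and each difference has variance 2σ².
- The correlation between endpoints is not given in the documents. A range of 0 to 0.9 is assumed.

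One endpoint null for both regimens needs no endpoint correlation. P(at least one rejection) = 2 × 0.05 − P(both reject) = 0.10 − 0.0093 = 0.0907. In favour of guselkumab only: 2 × 0.025 − 0.0046 = 0.0454, against a benchmark of 0.025. Both come from the bivariate normal distribution. The multi-endpoint rows below come from 1,000,000 multivariate normal draws with critical value 1.96.

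| True nulls among H15–H22 | Endpoint correlation | Any false rejection (two-sided) | In favour of guselkumab |
|---|---|---|---|
| One hypothesis only | – | 5.0% | 2.5% |
| One endpoint, both regimens | – | 9.1% | 4.5% |
| Two endpoints, both regimens | 0.9 | 12.6% | 6.3% |
| | 0.7 | 14.9% | 7.5% |
| | 0 | 17.3% | 8.9% |
| All four endpoints (eight tests) | 0.9 | 16.5% | 8.2% |
| | 0.7 | 22.6% | 11.4% |
| | 0 | 31.6% | 16.9% |

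For reference, eight fully independent tests would give 1 − 0.95⁸ = 33.7%, and the Bonferroni bound is 8 × 0.05 = 40%.

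**Binomial check.** ACR70 at Week 24 is rare enough for the normal approximation to matter. This check used 400,000 simulated trials, three arms of 150 with equal rates, and an unstratified chi-square in place of the stratified CMH:
- Rate 6% (PSA3001 placebo, Table 4): 8.6% two-sided, 4.2% in favour of guselkumab; a single test has size 4.8%.
- Rate 1.0% (PSA3003 placebo): 5.4% and 2.8%; a single test has size only 2.9%. The SAP's Fisher fallback would be lower still.

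**The case against.** The strongest reply is that the SAP discloses the weaker status. The qualification is in the same subsection as the claim. Table 4 and Appendix 10 label the tests weakly controlled, protocol 9.4.3 already separates the two tiers, and a footnote travels with every p-value. All of that stands and limits the harm. It does not make the 22-hypothesis sentence true. The footnote says that the tests lie outside the sequence, but not that family-wise control is absent.

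A second reply is that the eight do have control in the weak sense, so denying them family-wise control goes too far. The gate does hold the error at 5.0% when the primary null is true. It gives no protection once ACR20 is effective, and the corrected wording can say exactly that.

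A third reply is that the inflated figures need ACR20 at Week 24 to work while another ACR endpoint has exactly no effect at both regimens. The earlier studies in Table 4 show differences of 6 to 35 percentage points on all four endpoints. Zero correlation is also implausible, since every ACR70 responder at Week 24 is an ACR50 responder. This is fair. The zero-correlation and all-eight-null rows are outer limits, not forecasts. The one-endpoint figure does not depend on that correlation.

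On the gate, the singular wording leans towards matching each regimen to its own ACR20 result, and SAP Section 2 calls only H1 primary. The plural footnote and the Appendix 10 heading still leave the point open.

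**Conclusion.** The concern holds. The statements in SAP 5.3.3.1 and 5.3.3.2 are wrong as written: strong control at 5% covers H1–H14, not 22 hypotheses. The most defensible measure of the gap is 9.1% two-sided (4.5% in favour of guselkumab, against 2.5%) for one endpoint with no effect at either regimen. This assumes an effective ACR20 at Week 24, two-sided 0.05 per test and regimen correlation 0.5. For a rare response the gap nearly closes, as the 1.0% binomial case shows. With more null endpoints it widens by an amount that depends on an unknown correlation. The primary hypothesis, the study-success criterion and every test in Figure 2 are untouched.

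**What to change.** In SAP 5.3.3.1 and 5.3.3.2:
- Limit the 5% family-wise statement to H1–H14.
- Say that H15–H22 are prespecified tests gated on ACR20 at Week 24, without family-wise control once the gate is passed.
- Remove or qualify the statement that their p-values are not nominal.
- Give their test level, and say whether a regimen's tests need only its own ACR20 result or both regimens' results.
- Correct the cross-reference for the hypothesis list, which points to 6.11; the list is in 6.10.

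Align protocol 9.4.1 and the two matching synopsis sentences at the next amendment. No separate amendment is needed, because protocol 9.1 and 9.4.3 leave the method to the SAP. The cost is wording, and H15–H22 lose the claim of belonging to a 5% family. No test, decision rule or result for H1–H14 changes.

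Appending H15–H22 after MDA q8w would make the 22-hypothesis claim true, but it changes the decision rule for eight hypotheses and is not recommended. Taking the PSA3001/3002 powers in Table 4 for HAQ-DI q8w, FACIT-F (both regimens), MDA q4w and MDA q8w, and treating the other nine steps as certain, 0.97 × 0.87 × 0.93 × 0.99 × 0.78 = 0.61. Under independence, that is about a 39% chance that the eight are never tested. On the same inputs, any dependence gives between 22% (the largest single miss) and 46% (the sum of the misses).
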